# LIST OF ABBREVIATIONS

AE adverse event
CRF case report form
AF atrial fibrillation

**AFEQT** Atrial Fibrillation Effect on QualiTy-of-life Questionnaire

Questionnaire

#### 1. BACKGROUND

Transseptal puncture is a common procedure performed in the electrophysiology lab to facilitate catheter access and ablation in the left atrium or ventricle. This procedure is most commonly used for atrial fibrillation ablation, which requires two sheaths/catheters to be inserted into the left atrium. Puncture through the interatrial septum is typically facilitated using a needle, which is pushed through the fossa ovalis and into the left atrium. The major risk of transseptal puncture is inadvertent injury to the wall of the left atrium by the advancing needle and sheath assembly, potentially resulting in pericardial bleeding, cardiac tamponade, and even death.

#### 2. STUDY RATIONALE

Prior studies have shown that a radiofrequency (RF) transseptal needle is superior to a standard, manual needle with regard to left atrial access time. Recently, a novel RF wire system has been developed to further enhance the speed and safety of transseptal access. With this technique, an atruamatic RF wire can be used to both traverse the fossa ovalis and shield the left atrial wall from traumatic injury secondary to the advancing sheath. While this new RF wire system has recently become clinically available, there is no data substantiating its enhanced efficacy and safety compared to standard needle-based transseptal techniques.

#### 3. STUDY OBJECTIVES

Primary Objective: To determine if the Baylis Versacross RF wire results in a shorter time to successful transseptal puncture compared to the conventional Baylis RF needle.

Secondary Objectives:

To determine if the Baylis Versacross RF wire results in greater first attempt transseptal puncture success compared to the conventional Baylis RF needle.

To determine if the Baylis Versacross RF wire results in less complications compared to the conventional Baylis RF needle.

Version #: 1.1 Version Date: 08/26/20 Page 7 of 21

To determine if the Baylis Versacross RF wire results in less right atrial needle/wire exchanges compared to the conventional Baylis RF needle.

#### 4. STUDY DESIGN

This is a randomized, single blinded clinical trial comparing transseptal access using the Baylis Versacross RF wire versus the conventional Baylis RF needle among individuals undergoing atrial fibrillation catheter ablation.

Sedation, intubation, vascular access, and catheter ablation will be performed according to usual clinical care. Transseptal puncture will be performed using intracardiac ultrasound guidance. Each patient will undergo two transseptal punctures.

For participants randomized to the RF wire access system, the following equipment will be used:

- o VersaCrossTM RF Wire (Baylis, Montreal, Canada)
- o VersaCrossTM Transseptal Sheath (Baylis, Montreal, Canada)\*
- VersaCrossTM Steerable Sheath (Baylis, Montreal, Canada)\*

For participants randomized to the RF needle, the following equipment will be used:

- o NRG® transseptal needle (Baylis, Montreal, Canada)
- o SL1 sheath (Abbott Medical, Santa Clara, California).
- o Agilis steerable sheath (Abbott Medical, Santa Clara, California)

The primary endpoint is time to complete transseptal puncture. Timing will start when the transseptal sheath wire is inserted into the femoral vein short sheath and will stop when the transseptal dilator is removed from the long sheath after placement in the left atrium. For each transseptal, the number of unsuccessful attempts requiring rewiring will be recorded. Fluoroscopy time, fluoroscopy dose, number of RF applications, procedural complications, and total procedural time will also be determined.

Version #: 1.1 Version Date: 08/26/20 Page 8 of 21

\*Because the transseptal wire does not provide the same mechanical support as a RF needle, these sheaths and their accompanying dilators must be used with the RF wire.

At three months, six months, and one year after the ablation, study coordinators will follow up with participants and ask a series of questions remotely over the phone, or inperson if participants are coming to UCSF for clinical care. Total duration of subject participation will be one year.

#### 5. CRITERIA FOR EVALUATION

## Primary Efficacy Endpoint

• Time to completion of transseptal puncture

## **Secondary Efficacy Endpoints**

- Efficacy of transseptal puncture
- Number of right atrial needle/wire exchanges
- Procedural complications including:
  - i. Hemodynamically significant pericardial effusion
  - ii. Bleeding requiring surgical intervention or

transfusion

iii. Hypotension regarding prolonged pressor support after the procedure

- iv. Prolonged intubation required
- v. Air embolism
- vi. Peripheral embolic event
- vii. Stroke
- viii. TIA
- ix. Pseudoaneurysm\_
- x. AV fistula
- xi. Hematoma
- xii. Myocardial infarction
- xiii. Death
- xiv. Migraine
- Efficacy of catheter ablation procedures: time to first clinically evident sustained AF after employing a 3 month blanking period.

Version #: 1.1 Version Date: 08/26/20 Page 9 of 21

• Safety Evaluations: incidence of adverse events

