#### iii. Adverse Events

Information regarding occurrence of adverse events will be captured throughout the study. Duration (start and stop dates and times), severity/grade, outcome, and treatment will be recorded on the case report form (CRF).

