## Visit 3: Month 3 (post-study ablation)

- 1. Record any adverse events.
- 2. Record medications subject is currently taking.
- 3. Ask follow-up questions about migraines using CRFs.

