## Visit 4: Month 6 (post-study ablation)

- 1. Record medications subject is currently taking.
- 2. Ask follow-up questions about ablation procedure effectiveness using CRFs.
- 3. Administer AFEQT questionnaire.
- 4. Ask follow-up questions about migraines using CRFs.

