#### 11. ADVERSE EXPERIENCE REPORTING AND DOCUMENTATION

#### a. Adverse Events

An adverse event (AE) is any untoward medical occurrence in a clinical investigation of a patient. It does not necessarily have a causal relationship with the treatment. An AE is therefore any unfavorable and unintended sign (including an abnormal laboratory finding), symptom, or disease temporally associated with the administration of an investigational product, whether or not related to that investigational product. An unexpected AE is one of a type not identified in nature, severity, or frequency in the current Investigator's Brochure or of greater severity or frequency than expected based on the information in the Investigator's Brochure.

The Investigator will probe, via discussion with the subject, for the occurrence of AEs during each subject visit and record the information in the site's source documents. Adverse events will be recorded in the patient CRF. Adverse events will be described by duration (start and stop dates and times), severity, outcome, treatment and relation to study intervention, or if unrelated, the cause.

Version #: 1.1 Version Date: 08/26/20 Page 13 of 21

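### The AF-recurrence endpoint turns on a Month 3 boundary, but no AF or effectiveness question is listed at the Month 3 contact and no source for dating AF is named

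*Combined protocol and SAP*

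**What the plan says.** Section 5 (Secondary Efficacy Endpoints) measures ablation efficacy as "time to first clinically evident sustained AF after employing a 3 month blanking period". Section 4 schedules contacts at three months, six months and one year, at which coordinators "ask a series of questions remotely over the phone", or in person if the patient is attending for care.

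Section 10 sets out the contents of each contact:

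- **Month 3 (Visit 3):** "Record any adverse events", "Record medications subject is currently taking" and "Ask follow-up questions about migraines using CRFs". Nothing else is listed.
- **Month 6 (Visit 4):** "Ask follow-up questions about ablation procedure effectiveness using CRFs" appears for the first time, alongside medications, the AFEQT and migraine questions.
- **Month 12 (Visit 5):** the same effectiveness item appears again.

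Appendix 1 marks only adverse experiences at Month 3. It has no effectiveness row at any visit, and its diary rows are unmarked. No ECG, ambulatory monitor or chart review is specified for AF recurrence.

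On adverse events, Section 11.a says "The Investigator will probe, via discussion with the subject, for the occurrence of AEs during each subject visit". Sections 9.a.iii and 11.a both require start and stop dates for each event.

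**The concern.** The blanking rule makes the date of an episode decide whether it is an event. The schedule has a contact at the end of blanking, when recent episodes would be easiest to place, but does not list the question there. The first effectiveness interview then looks back over both the blanked months and the first three countable months.

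Two errors can follow. An episode at week 10 may be remembered as about three months after the procedure and counted as a recurrence. An episode at week 15 may be remembered as early and discarded. Either one changes a patient's event status or event time in a trial of at most 72 patients. What the patient could have said at Month 3 is hard to recover at Month 6.

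**Working it through.** **1. The plan's own figures.** None is given for AF recurrence. The only calculated figure is the 99% power for transseptal time in Section 13.d. Reading the stated 5 minutes as a between-group difference, with SD 5 and 36 per arm (1:1 assumed): 5 / (5 × √(2/36)) − 1.960 = 4.243 − 1.960 = 2.283, and Φ(2.283) = 98.9%. That agrees with the plan. The present point does not depend on it.

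**2. Boundary against schedule.**

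| Contact | AF or effectiveness question listed | Period since ablation |
|---|---|---|
| Month 3 | none | months 0–3, all blanked |
| Month 6 | yes, first time | months 0–6: half blanked, half countable |
| Month 12 | yes | later follow-up, all countable |

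An episode close to Month 3 is thus first asked about, as an effectiveness question, roughly 6 − 3 = 3 months after it happened.

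**3. Does the Month 3 adverse-event question fill the gap?** In part. Events reported then would carry dates. But nothing says that AF recurrence is to be recorded as an adverse event, and effectiveness has its own CRF questions. Migraine is a useful comparison. It is a listed complication in Section 5, yet Visit 3 asks about it specifically in addition to the adverse-event item. AF, the outcome with a Month 3 cut-off, gets no such question.

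**4. How sensitive is classification to dating error?** Assumptions, none from the documents: one episode, uniformly distributed over 26 weeks; boundary at week 13; normal dating error with standard deviation s. An episode d weeks from the boundary lands on the wrong side with probability 1 − Φ(d/s).

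| s (weeks) | d = 2 weeks | average over 0–26 weeks |
|---|---|---|
| 2 | 1 − Φ(1.00) = 16% | 6% |
| 4 | 1 − Φ(0.50) = 31% | 12% |
| 6 | 1 − Φ(0.33) = 37% | 18% |

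The risk is concentrated near the boundary.

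**5. In patients.** Assume 20–40% of 72 have AF in the first three months and 10–20% of those are placed on the wrong side.

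- Low: 72 × 0.20 × 0.10 = 1.4
- High: 72 × 0.40 × 0.20 = 5.8

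That is about 1 to 6 patients. The count covers early episodes moved late, not late episodes moved early. A patient with AF both before and after Month 3 is a true event either way; only the event time changes. The range is therefore an order of magnitude, not an estimate of changed event status.

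**The case against.** The strongest reply is that nothing in the protocol says dates come from memory. The endpoint is clinically evident AF, which may be documented in care records. Source documents are kept for each subject, some follow-up may be in person, and the CRFs are not shown; they may ask for dates or documentation. A reader might infer that patients must recall their episodes at Month 6. The documents do not support that. What they support is narrower: no dating source is named, so as written the dating would rest largely on recall.

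Second, Month 3 is not empty. The adverse-event definition in Section 11.a is broad, no text excludes AF from it, and a hospitalization for AF would be a serious event collected through the final visit. This stands as a partial, dated route. It is not AF-specific and so cannot be relied on for completeness.

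Third, Appendix 1 is weak evidence. It also lacks a migraine row and leaves medication review unmarked, although Section 10 requires both. The point therefore rests on the visit lists in Section 10.

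Fourth, AF recurrence is one of several secondary endpoints, is absent from the objectives in Section 3, and has no analysis in Section 13. This limits the importance of the point but does not remove it.

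**Conclusion.** The mismatch holds on the text. The endpoint is cut at Month 3, the Month 3 contact lists no AF or effectiveness question, and no monitoring or record source is named for dating. It deserves correction mainly because correction is cheap.

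Two larger readings should be resisted:

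- **A quantified distortion.** Setting 1.4–5.8 patients against an assumed 25% recurrence (72 × 0.25 = 18) gives 8–32%, and a reader might infer that this share of recurrences would be wrong. Every input is assumed, and the sum ignores patients with AF on both sides of Month 3. The documents support no figure beyond perhaps a few patients.
- **Bias between arms.** Patients are blinded (Section 8), so dating error is probably similar in the two arms and mainly adds noise. Research staff know the assignment, so similarity is likely rather than assured, but the documents do not show a directional effect.

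The primary endpoint is timed during the procedure and is unaffected.

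**What to change.** 1. Add the existing ablation-effectiveness questions to Visit 3 in Section 10, and add an effectiveness row to Appendix 1 for Months 3, 6 and 12. At Month 3, record the date of each AF episode to that contact and whether AF is present at the contact.
2. At Visits 4 and 5, ask for dated AF since the previous contact.
3. Classify each episode by its own date relative to 3 months after ablation, not by the date of the Visit 3 contact. For example, if that contact happened at week 15, an episode at week 14 would already be countable. If Visit 3 took no dates and Visit 4 asked only about the time since, that episode would be lost.
4. State the source used to date recurrence. If clinical records are intended, say so.

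The cost is a few extra minutes of coordinator and patient time at a contact already scheduled, with no new visit, test or patients. The six-month recall between Months 6 and 12 remains, but it does not cross the blanking boundary.

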#### 6. SUBJECT SELECTION

a. Study Population

Subjects with a diagnosis of atrial fibrillation or atrial flutter undergoing endocardial left atrial catheter ablation procedures who meet the inclusion and exclusion criteria will be eligible for participation in this study.

- b. Inclusion Criteria
- 1. Age  $\geq$  18 years
- 2. Patients undergoing endocardial left atrial catheter ablation procedures using radiofrequency ablation catheters for atrial fibrillation or atrial flutter ablation procedures at UCSF
- 3. Willing and able to provide written informed consent in English.
- 4. Willing and able to comply with scheduled remote follow-up visits (through Year 1)
  - c. Exclusion Criteria
- 1. Presence of a patent foramen ovale closure device or atrial septal defect closure device.
- 2. Cryoballoon ablation
- 3. IVC filter
- 4. Deemed not suitable by study personnel.

#### 7. CONCURRENT MEDICATIONS

a. Allowed Medications and Treatments

Standard pharmacologic therapy for atrial fibrillation or atrial flutter is allowed. There are no prohibited medications.

#### 8. STUDY TREATMENTS

a. Method of Assigning Subjects to Treatment Groups

Up to 72 eligible patients will be randomly assigned to either the (1) RF wire group or (2) RF needle group for transseptal puncture. The randomization codes will be generated prior to the start of enrollment using a computer program to create randomization assignments to either group 1 or group 2, using blocks of 6.

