## **Blinding**

The randomization assignments will not be known to patients. However, due to the nature

Version #: 1.1 Version Date: 08/26/20 Page 10 of 21

of the study, investigators and research staff will need to know the randomization

assignments since investigators will be performing the ablation procedures using devices specific to each randomization group.

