#### 10. EVALUATIONS BY VISIT

## Visit 1: Screening

- 1. Review the study with the subject and obtain informed consent and HIPAA authorization and assent through written paper form or DocuSign.
- 2. Assign the subject a unique screening number.
- 3. Record demographics data.
- 4. Record medical history.
- 5. Record medications subject is currently taking.
- 6. Administer Atrial Fibrillation Effect on QualiTy-of-life questionnaire.
- 7. Ask questions about migraines using CRFs.
- 8. Randomize subject after completion of this visit, 1 day before ablation procedure.

Version #: 1.1 Version Date: 08/26/20 Page 12 of 21

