## 12.4 Replacement of Subjects

Subjects who do not undergo the study ablation procedure will be replaced.

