#### 13. STATISTICAL METHODS AND CONSIDERATIONS

## a. Data Sets Analyzed

All subjects who undergo a transseptal puncture during their study ablation procedure will be included in the analysis.

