## d. Sample Size and Randomization

The sample size of seventy-two patients will provide 99% power to detect a stastically significant difference in time assuming mean transseptal time of 5 minutes and standard deviation of 5 minutes using a two-tailed alpha of 0.05.

Up to 72 eligible patients will be randomly assigned to either the (1) RF wire group or (2) RF needle group for their transseptal puncture. The randomization codes will be generated prior to the start of enrollment using a computer program to create randomization assignments to either group 1 or group 2, using blocks of 6.

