# **APPENDIX 1: SCHEDULE OF STUDY VISITS**

	VISIT 1 (Screening)	VISIT 2 (Ablation Procedure Day)	VISIT 3 (3 Month (post-study ablation))	VISIT 4 (6 Months (post-study ablation))	VISIT 5 (1 Year (post-study ablation))
Informed Consent	X	I I I	I I I		
Medical History	X	 	 	 	
Complete Physical Exam		 	 	 	
Abbreviated Physical Exam		 	I I I	 	
Height		T 1 1	T 	 	
Weight		 	T I I		
Vital Signs		 	 	 	
Oximetry		 	 	 	
Spirometry		 	I I I	 	
Pharmacokinetics		 	 		
Chemistry		 	T I I		
Pregnancy Test (Urine or Serum)		 	 	 	
Hematology		 	 	 	
ESR		 	I I I	 	
C-Reactive Protein		T 1 1	T I I	I I I	
Urinalysis		] 	 	] 	
Randomization	X (DAY BEFORE ABLATION)				
Dispensing or Administration of Study Drug					
Counting of Returned Study Drug					
Initiate Subject Diary					
Subject Diary Review					
Concomitant Medication Review					

Adverse Experiences		X	X	X	X
AFEQT	X			X	X

a □2 days

- 2. Ross J, Jr. Transseptal left heart catheterization a 50-year odyssey. *J Am Coll Cardiol.* 2008;51(22):2107-2115.

Version #: 1.1 Version Date: 08/26/20 Page 21 of 21

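### One printed block size of 6 makes about a quarter of assignments predictable to unblinded staff, and replacing unablated patients while analysing only punctured ones could hide arm-dependent loss and complete access failure

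*Combined protocol and SAP*

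**What the plan says.** **Allocation.** Section 8.a states that codes are produced by computer before enrolment to "create randomization assignments to either group 1 or group 2, using blocks of 6". Section 13.d repeats the block size and the ceiling: "Up to 72 eligible patients will be randomly assigned". Neither states the allocation ratio, who holds the list, or how each code is released.

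**Who knows, and who decides entry.** The Blinding section keeps patients unaware but says that "investigators and research staff will need to know the randomization" assignments. Inclusion criterion 2 limits enrolment to one centre. The last exclusion criterion is open-ended: "Deemed not suitable by study personnel".

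**Timing.** Visit 1 says: "Randomize subject after completion of this visit, 1 day before ablation procedure". Appendix 1 agrees.

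**After assignment.** Section 12.4: "Subjects who do not undergo the study ablation procedure will be replaced". Section 13.a: "All subjects who undergo a transseptal puncture during their study ablation procedure will be included in the analysis". No set of all randomized patients is defined, and no by-arm report of those left out is planned.

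**The endpoint.** Section 4 stops the clock only when the dilator comes out of a sheath already in the left atrium, so completely failed access yields no time. Section 4 also records the number of failed attempts that need rewiring. First-attempt success is a secondary objective (Section 3), and efficacy of puncture is a secondary endpoint (Section 5).

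**The concern.** There are two separate openings.

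Before assignment, the people who know past assignments and the block size may also be those who judge suitability. When the next code is known or likely, a patient expected to be difficult could be turned away from one arm more often than from the other. The primary endpoint is an operator-dependent time in a comparison that is not blinded to the operator.

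After assignment, at least a day passes in which a procedure can be cancelled, possibly with the arm known; the Blinding section does not say when staff are told. A cancelled patient has no transseptal time, so leaving that patient out of the time analysis is unavoidable. But replacement without a by-arm count means that the planned report would not show losses that differ by arm. A patient in whom access is tried and never achieved can also be read out of the analysis set. In a comparison of access devices, that is an outcome rather than missing data.

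**Working it through.** **1. The plan's own figure.** Section 13.d states 99% power with 72 patients, SD 5 min and two-sided alpha 0.05. With 36 per arm and 5 min read as the between-arm difference: 5 / (5 × √(2/36)) = 4.243; 4.243 − 1.960 = 2.283; Φ(2.283) = 98.9%. It reproduces on that reading. Losing 2, 4 or 8 per arm without replacement would leave 98.5%, 97.9% or 96.3%, so at that difference power does not depend on replacement.

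**2. Predictability of a fixed block of 6.** Input: block of 6 (Sections 8.a and 13.d). Assumption: 1:1, so 3 and 3. There are 20 equally likely sequences.

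| Position | P(certain in advance) | P(best guess right) |
|---|---|---|
| 1 | 0 | 0.5 |
| 2 | 0 | 0.6 |
| 3 | 0 | 0.6 |
| 4 | 2/20 = 0.1 | 0.7 |
| 5 | 8/20 = 0.4 | 0.7 |
| 6 | 1 | 1 |
| Sum | 1.5 | 4.1 |

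Certain: 1.5/6 = 25%. Over 72/6 = 12 blocks, that is 18 patients. Best guess right: 4.1/6 = 68.3%.

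**3. Varied blocks.** In 4,000 simulated lists of 72 with sizes 4, 6 and 8 mixed at random, and a guesser who knows the set of sizes, 2.3% of assignments are certain (0.023 × 72 ≈ 1.7 patients) and best guessing is right 67.8% of the time. Certainty nearly disappears; guessing hardly changes.

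**4. Size of the bias, with no true effect.** From Section 13.d: mean 5, SD 5. Assumptions: lognormal times, so the log-scale SD is √ln 2 = 0.833; correlation r = 0.3 to 0.5 between the staff's prediction and log time. If the fraction f predicted longest is removed, the mean of those left falls by

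5 × [1 − Φ(z₁₋f − 0.833r) / (1 − f)].

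*Before assignment.* Staff turn away the top 10 to 20% when one given arm is the best guess. A block offers a strict best guess at 3.8 positions (0 + 1 + 0.4 + 1 + 0.4 + 1), half of them for that arm: 1.9 × 12 = 22.8 positions. The guess is right at 3.0 of 3.8, so 18 screened patients go to that arm and 4.8 to the other. The net weight is (18 − 4.8)/36 = 0.367. Turned away: 22.8 × f/(1 − f) = 2.5 to 5.7 patients.
- f = 0.1, r = 0.3: 5 × (1 − 0.8489/0.9) = 0.284; × 0.367 = 0.10 min.
- f = 0.2, r = 0.5: 5 × (1 − 0.6647/0.8) = 0.846; × 0.367 = 0.31 min.

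Simulation (40,000 runs) gives 0.10 to 0.31 min, with false positives of 4.7 to 5.4% (t-test) and 5.1 to 5.7% (Wilcoxon). With varied blocks the shift is still 0.11 to 0.30 min. If staff act only on certain assignments, it is 0.07 to 0.20 min with blocks of 6 and 0.00 to 0.02 min with varied blocks.

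*After assignment.* Two or three of 36 in one arm, those predicted longest, are lost and replaced. Taking patients one at a time with f = k/36:
- k = 2, r = 0.3: 5 × (1 − 0.9104/0.9444) = 0.18 min.
- k = 3, r = 0.5: 5 × (1 − 0.8332/0.9167) = 0.46 min (0.45 in simulation).

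False positives are 4.7 to 6.2% (t-test) and 5.2 to 6.2% (Wilcoxon). Removing the top two or three by rank instead gives 0.16 to 0.40 min, with 4.8 to 5.9% and 5.2 to 6.1%.

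With no selection the tests reject in 4.5 to 4.6% (t-test) and 4.9 to 5.0% (Wilcoxon).

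**5. Sections 12.4 and 13.a side by side.** Replacement is triggered by no ablation; analysis is triggered by a puncture. A patient punctured but not ablated is therefore both analysed and replaced. A patient with complete access failure is replaced if not ablated and, read literally, not analysed. If 1 or 2 of 36 in one arm had such a failure (2.8 or 5.6%), a punctured-only set would show none. The documents give no expected rate.

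**The case against.** The strongest reply is that the effect is small and rests on assumptions. The correlation, the fraction turned away, the number lost and the 1:1 ratio are not in the documents, and nothing there shows that staff can predict transseptal time. That stands.

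Randomization also follows completion of screening, and the protocol refers to a study manual that is not available here, so a concealed release may exist. That stands too: silence about release mechanics alone would be only missing detail. What is on the page, however, is the fixed block size, printed twice.

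Varied blocks do little against guessing, and unblinded staff will still know past assignments. This is correct. The gain is confined to assignments that are certain.

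Part of the loss could be reconstructed: withdrawal reasons go to source documents (Section 12.3), and serious adverse events are collected from consent (Section 11.b). That is true, but it is not a planned report by arm.

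Three stronger readings are tempting and not supported. One is that first-attempt failures vanish. They do not: a patient crossed on a later attempt has had a puncture, stays in the set, and has the failed attempts recorded under Section 4. The second is that the rules will hide differential loss. The documents show an opportunity, not an occurrence. The third is large error inflation. If the longest observed times in one arm were removed and replaced, t-test error would be about 8 to 11% with two losses and 14 to 22% with four. But nobody could know those times before the procedure.

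**Conclusion.** The point holds as a worthwhile, low-cost improvement and not as a threat to the trial's main conclusion. With a fixed block of 6 and 1:1 allocation (assumed), about 18 of 72 assignments can be known in advance, against about 1.7 with mixed blocks of 4, 6 and 8. Under the assumed selection the mean shifts by about 0.1 to 0.45 min, which is 2 to 9% of the planned 5-minute mean, and two-sided error stays at or below about 6%. The analysis-set rule matters more for the device-success outcomes than for the time test: read literally, it drops complete access failures, whose number cannot be estimated from the documents. The mismatch between Sections 12.4 and 13.a is in the text and depends on no assumption.

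**What to change.** 1. **Sections 8.a and 13.d.** State the allocation ratio. Use randomly varied block sizes, for example 4, 6 and 8, and keep them out of the protocol that staff hold. Release each assignment only after eligibility and suitability are recorded. This cuts certain assignments from 25% to about 2% but leaves best guessing at about 68%.
2. **Section 13.a.** Analyse all randomized patients in whom transseptal access is attempted, in the assigned arm, including after failed access or a device switch. Report by arm, with reasons, those randomized but not attempted. Set in advance one rule for failed access that works with the primary test, for example worst rank with the Wilcoxon test as the primary analysis if any access fails; worst rank does not fit the t-test that Section 13.c also allows. Since Section 4 plans two punctures per patient, say whether failure of one counts. Do not apply the rule to cancelled procedures.
3. **Sections 12.4 and 13.a.** Reconcile the ablation and puncture triggers, so that a patient with attempted access is not both analysed and replaced. Say how replacements fit under the ceiling of 72.
4. **Optional, Visit 1 and Appendix 1.** Randomize on the procedure day, so that most cancellations come before assignment.

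Cost: a new list, a simple release step and protocol wording. Item 4 needs both device kits at hand for each case; if that is impractical, items 1 to 3 stand without it.
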